### **9.7.1 Main analysis**

Comparative analysis for primary and secondary outcomes will be conducted between treatment groups. The comparative analysis will follow a two-step approach. The first step will compare the baseline characteristics and clinical outcomes of individual NOAC (Dabigatran, Rivaroxaban) -versus warfarin-treated groups.

[figure not shown]
During the first step of the comparative analysis, the baseline characteristics of the individual NOAC groups will be balanced with the warfarin group to account for potential confounding effects. Propensity scores will be calculated based on multinomial logistic regressions, with all covariates being incorporated. Next, an inverse probability of treatment weighting (IPTW) method will be applied using the calculated propensity score to avoid sample size inflation and to ensure appropriate estimation of variances. Yet, the IPTW estimates can be heavily influenced by large weights, thus destabilizing the results. To increase the robustness of the model, weight truncation will be applied once the distribution of propensity score is available. The distribution of propensity scores will be described, based on which the cut-off points of weight estimates will be chosen. Lastly, the calculated stabilized IPTW (s-IPTW) estimates will be applied to obtain two comparative pairs of individual NOAC vs. warfarin groups, for which the baseline demographics, risk factors, and clinical characteristics will be compared

using the absolute standardized difference (ASD) pre- and post- IPTW to assess the balance and model robustness. A covariate (baseline demographics, risk factors, clinical characteristics) will be considered well balanced if the ASD is below 0.1.

A Cox proportional hazard regression model with the time since NOAC drug index date as the underlying timescale will be used to compute adjusted hazard ratios (aHRs) with 95% CIs. If substantial covariate imbalance between treatment group is noted assessed by a standardized difference  $>0.1$ , then outcome models will be further adjusted by covariates that are out of balance using multivariable Cox proportional hazards models.

The second step will determine whether the patient characteristics are comparable between dabigatran and rivaroxaban treatment groups and whether there is the required sample size for comparisons between dabigatran- and rivaroxaban-treated groups. If the database can fulfil the sample size requirement, analysis will move forward for comparative analysis between the two NOAC groups.

For each component outcome of all 3 groups, the event-free survival will be plotted with Kaplan-Meier curves after s-IPTW adjustments.

### **9.7.3 Safety Analysis**

Please refer to the other analysis sections.

## **9.8 QUALITY CONTROL**

The quality control, review, and monitoring plan are summarized below. Greater details are documented in the NIS-DMRP.

The study will strictly follow BI NIS SOP, PASS SOP and any other relevant SOPs. In addition, this study will follow key elements of the Guideline for Good Pharmacoepidemiology Practices (GPP) and Good Pharmacovigilance Practice (GVP). The statistical analytic approach will be reviewed/repeated by a second analyst. The study report will be reviewed, approved and archived per BI SOP.

Whenever possible, validated algorithm will be used for variables, including exposure, outcomes, and covariates, to minimize misclassification and information bias.

One Analyst from [REDACTED] will build measures (variables) for cohort inclusion, exposures, outcomes and covariates. All measures created, cohorts developed, statistical analyses implemented, and tables output will undergo quality control review performed by at least 1 additional Analyst from [REDACTED].

Quality controls include checks for the validity and logical content of codes and checks for missing values and variables.

The Analyst from BI assigned to the study will perform a cross-review of the different tables of results.

In order to control for potential inconsistencies and errors, all variables will be tabulated. The distribution of each variable will be examined. Extreme observations with values larger than  $\pm 3$  standard deviations (SD) will be examined as potential outliers and consequently excluded from the dataset.

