## **9.2 SETTING**

**Study Period:** the entire time period that includes the look-back period, the cohort entry date (drug index date), and follow-up period for the study population. The study period will be from April 18th, 2011 (start of data collection) to December 31st, 2020 (end of data collection).

**Patient Selection Period:** the time period for which patients are eligible to enter the cohort, which is from April 18th, 2012 to December 31st, 2020.

**Cohort Entry Date:** The drug index date, defined as the first date of prescription for dabigatran, rivaroxaban, or warfarin during the patient selection period.

**Look-back Period:** the 365-day period that ends 1 day prior to the cohort entry date. The earliest start date of the look-back period is April 18th, 2011.

**Loss of follow-up:** the last data point available in the database during the study period.

**Follow-Up Period:** the period starting from the cohort entry date (first prescription of the drug of interest) and ending at the earliest occurrence of the following:

- Discontinuation of the index OAC, defined as a continuous gap of 45 days or more between the expected refill date and the actual refill date (discontinuation date defined as 45 days after the expected refill date)
- Switching to another OAC, if the index OAC is discontinued and another OAC is started within 45 days of the expected refill date of the index OAC
- Loss of follow-up
- Occurrence of outcomes of interest (for primary outcome: major bleeding; for secondary outcome: the onset of the first occurring component event; for further outcomes: the respective onset of component events)
- Death (except for analyses for the composite outcome and all-cause mortality as a component outcome)
- End of study period

The notion of enrollment is not defined in [REDACTED]. Therefore, a proxy enrolment criterion defined as start of enrolment = date of first inpatient/outpatient encounter; end of enrolment = date of last inpatient/outpatient encounter will be used. "Enrolment" herein will refer to this proxy enrolment measure. For entry into the study population, patients will be required to have had at least 365 days of enrollment prior to the cohort entry date.

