## **9.5 STUDY SIZE**

During the period from April 2011 to December 2020, there are roughly 17000, 11000, and 4000 NVAF adult patients with a medical history of CAD being respectively treated with either warfarin, rivaroxaban or dabigatran as the first OAC (defined as no history of OAC usage during the 12-month look-back period) within the [REDACTED] database.

According to a published paper based on the [REDACTED] database, the mean (standard deviation, SD) treatment duration of different drugs among new user groups ranged from 265 (263.8) to 868 (725) days, with the dabigatran group exposed to the treatment the longest [P20-03503]. According to the same article, the major bleeding rate for AF patients is 1.5 per 100 patient-years. In comparison, AF patients with concomitant CAD are more likely to fall under high or medium/high risk categories of the HAS-BLED score, a predictor of bleeding complications among AF patients, thus increasing the event rate for major bleeding about 2-3 times [P09-11669], [R11-4223]. Therefore, the major bleeding rate is assumed to be rather 3-4.5 per 100 patient-years among Japanese AF+CAD patients in the [REDACTED] database.

Furthermore, previous analysis concluded substantial superiority of dabigatran (HR=0.66, 95% CI 0.529-0.825) and rivaroxaban (HR=0.74, 95% CI 0.618-0.879) over warfarin in major bleeding among AF patients [P09-11669], [R11-4223]. The comparative rates of major bleeding between individual NOAC- and warfarin- treated patients should follow a similar trend among NVAF patients with concomitant CAD.

For dabigatran vs. warfarin, if the HR is assumed to be 0.66 and the average exposure time to be 1 year per patient, an event rate of 3 per 100 patient-years with 80% power will require a total sample size of 6050 patients and 3025 patients for each arm; an event rate of 4.5 per 100 patient-years will require a total sample size of 4040 patients and 2020 patients for each arm. To be conservative, the lower bound is selected and therefore each arm needs around 3025 patients.

Similarly, assuming the HR of rivaroxaban vs. warfarin is 0.74 and the average exposure time to be 1 year per patient, the lower-bound event rate of 3 per 100 patient-years with 80% power will require a total sample size of 9690 patients and 4845 patients for each arm.

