### **10.3 HANDLING OF INCONSISTENCIES IN DATA AND OUTLIERS**

For lab values, distribution of each variable will be assessed. The extreme outliers will be treated as missing values, approaches to handling missing values are described in the previous section.

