**12. QUALITY CONTROL**

Please check section 9.8 of the study protocol

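### Protocol 9.8 excludes observations for lying beyond ±3 SD, with no exception for plausible values, and SAP 10.3 gives a different rule for laboratory values; the two need to become one rule that only flags

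*Protocol*

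**What the plan says.** Protocol 9.8 (Quality Control) states that "all variables will be tabulated. The distribution of each variable will be examined". Observations more than 3 SD from the mean "will be examined as potential outliers and consequently excluded from the dataset". The sentence does not limit the rule to a type of variable, require an error to be shown, or exempt plausible values. It does not say whether the single value or the whole patient is dropped, or whether the SD is calculated within each drug group or over all patients.

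SAP 10.3 covers laboratory values only and takes a different action: "The extreme outliers will be treated as missing values". It does not define extreme. SAP 10.2 then keeps a patient with a partly missing variable in the analysis through a missing-data category.

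SAP 12 (Quality Control) consists of one line: "Please check section 9.8 of the study protocol". SAP 5 records no amendments.

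**The concern.** An outlier rule should remove errors. A 3 SD limit removes the tail of a distribution whether or not the values are true, and in a skewed variable the tail is largely real patients. Follow-up time is such a variable, and it is the denominator of every rate and the time axis of the Cox model. Dropping patients for long follow-up is selection on something that happens after the index date. Weights built from baseline covariates cannot undo it, and Protocol 9.5 says that treatment duration differs by drug.

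Laboratory values matter too. Creatinine, liver enzymes and bilirubin feed the HAS-BLED score (SAP 8.3), which is a covariate in the propensity model (SAP 11.1 and Annex 4). High values are the ones that score the point, and an outlier rule acts on that same tail. Under Protocol 9.8 they are excluded; under SAP 10.3 they become missing.

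Two analysts who follow the documents could therefore arrive at different cohorts, person-time and hazard ratios for the primary safety comparison.

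**Working it through.** The plan gives no figure for how many observations the rule would remove, so there is nothing to reproduce. The size below is an illustration.

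**Inputs**
- Protocol 9.5, from the cited AF cohort: mean (SD) "treatment duration of different drugs among new user groups ranged from 265 (263.8) to 868 (725) days", dabigatran being the longest.
- Protocol 9.2: the patient selection period, "which is from April 18th, 2012 to December 31st, 2020". That is 3,179 days, the longest possible follow-up.
- Protocol 9.5: about 17,000 warfarin, 11,000 rivaroxaban and 4,000 dabigatran patients; 3,781 dabigatran patients needed (3,025/0.8).

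**Assumptions (not in the documents):** durations follow a gamma distribution with shape k = (mean/SD)² and scale θ = SD²/mean; a flagged patient is dropped entirely; the cut stays at the stated mean + 3 SD. Patients lost = P(D > cut). Person-time lost = the tail beyond the cut of a gamma with shape k + 1. For end-of-study censoring, assume uniform entry over 3,179 days, so that S(t) = P(D > t) × (1 − t/3,179). Patients lost are then S(cut), and person-time lost is [cut × S(cut) + ∫S from cut to 3,179] / ∫S from 0 to 3,179.

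**SD within group, 265 (263.8) days**
- k = 1.009, θ = 262.6; cut = 265 + 3 × 263.8 = 1,056 days.
- Without end-of-study censoring: 1.83% of patients, 9.1% of person-time.
- With censoring: 1.83% × (1 − 1,056/3,179) = 1.2% of patients; 6.5% of person-time.

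**SD within group, 868 (725) days**
- k = 1.433, θ = 605.6; cut = 868 + 3 × 725 = 3,043 days.
- Only patients who enter in the first 3,179 − 3,043 = 136 days could exceed it.
- The uncensored tail of 1.61% cannot be used: 1.31 of those percentage points lie beyond 3,179 days.
- With censoring: 1.61% × (1 − 3,043/3,179) = about 0.07% of patients; about 0.3% of person-time.

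**SD pooled over drugs (a deliberate extreme: warfarin and rivaroxaban both at 265 (263.8), dabigatran at 868 (725))**
- Mean = (28,000 × 265 + 4,000 × 868)/32,000 = 340.4 days.
- Variance = [28,000 × (263.8² + 75.4²) + 4,000 × (725² + 527.6²)]/32,000, so SD = 407.9.
- Cut = 340.4 + 3 × 407.9 = 1,564 days.
- Without censoring: about 0.3% of warfarin and rivaroxaban patients and 14.7% of dabigatran patients.
- With censoring, multiply by 1 − 1,564/3,179 = 0.508: about 0.1% and 7.5%.
- Dabigatran patients left: 4,000 × (1 − 0.147) = 3,412, or 4,000 × (1 − 0.075) = 3,700. Both are below 3,781.

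Whether the SD is pooled or taken within group thus decides which group bears the loss, and Protocol 9.8 does not say.

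**The case against.** The strongest reply is that SAP 10.3 is the later and more specific text. It deals with outliers by name, confines itself to laboratory values and, with SAP 10.2, keeps the patient in. On that view SAP 12 is only a general pointer to the quality-control section. This is a fair reading, but the documents do not settle it. SAP 10.3 neither withdraws the protocol sentence nor mentions non-laboratory variables, and SAP 12 refers the analyst to Protocol 9.8 without reservation.

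Protocol 9.8 also says that values are examined first, and that details are in the data management and review plan, which is not among the documents reviewed. That plan may set out how flagged values are judged. The protocol sentence nevertheless moves from examination to exclusion with no step in which a plausible value is kept. It is also true that follow-up is a derived quantity which an analyst might not screen at all; the text does not exempt it.

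A reader might go further and infer that the rule deletes outcome events. For a yes/no variable with prevalence p, a yes lies √((1 − p)/p) SD above the mean, which exceeds 3 whenever p is below 10%. Protocol 9.5 says "the major bleeding rate is assumed to be rather 3-4.5 per 100 patient-years" and takes "the average exposure time to be 1 year per patient". The event proportion is then 1 − e^(−0.03) = 3.0% to 1 − e^(−0.045) = 4.4%, and an event lies 5.7 to 4.7 SD out. The arithmetic is right, but the documents do not support the inference. Protocol 9.7 plans SDs for continuous variables only and has categorical ones summarised as counts and percentages. The planned rates and Cox models also require those events to be counted. The literal scope of all variables is loose drafting, probably not an intention.

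**Conclusion.** Wrong as written, and it should be fixed before the analysis. Protocol 9.8 instructs exclusion for distance from the mean alone. SAP 10.3 conflicts with it for laboratory values and leaves it standing for other continuous variables.

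The size is uncertain and depends on choices that the text leaves open. With the SD within group and whole-patient exclusion, it is about 1.2-1.8% of patients and 6.5-9.1% of person-time at 265 (263.8) days, and close to nil at 868 (725) days. With pooled SDs the loss could fall mainly on the longest-treated group; the 7.5-14.7% above is an extreme case, not a forecast. All of this rests on a gamma shape and on durations from a cited AF cohort, not from this study. In practice the study's own means and SDs would set the cuts, so the losses could be larger or smaller. If only the value is dropped, the effect depends on how the gap is then handled.

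It would be too strong to say that the plan removes valid patients outright, since the text leaves open whether a patient or a value goes. Nor does it establish that primary events would be deleted, for the reasons given above.

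**What to change.** Replace the last sentence of Protocol 9.8 with a rule of this kind: values beyond ±3 SD are flagged and checked; only impossible values (for example negative durations, or laboratory results outside the measurable range) or values verified as erroneous are set to missing; no patient, outcome event, covariate value or follow-up time is removed for distance from the mean alone. Make SAP 10.3 state the same rule, for laboratory and other variables alike, so that the reference in SAP 12 leads to a single instruction. The data management and review plan should be checked for consistency.

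The cost is one sentence in each document, with no new data and no added analysis.

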## **9.9 LIMITATIONS OF THE RESEARCH METHODS**

This is a non-interventional study based on existing data. The data do not include vital signs or laboratory test results (e.g. blood pressure, international normalized ratio values, renal function parameters). Therefore, the study may be subject to potential residual confounding due to the absence of certain key data.

Further, the [REDACTED] database contains around 23% of emergency care hospitals in Japan, which does not form a fully closed healthcare system and therefore could lead to information bias.

Additionally, the mortality is only known for hospitalized patients during hospitalization, thus resulting in inaccurate estimates of the mortality rate.

Due to the above reasons, the study results might not be generalizable to the entire AF patient population in Japan.

## **9.10 OTHER ASPECTS**

Not Applicable.

### **9.10.1 Data quality assurance**

The quality assurance auditor will have access to the investigator's study-related files and correspondence of this study.

### **9.10.2 Study records**

#### **9.10.2.1 Source documents**

Source documents provide evidence for the existence of the patient and substantiate the integrity of the data collected. Source documents are filed at BI.

#### **9.10.2.2 Direct access to source data and documents**

All source documents must be available at all times for review by BI, IRB/IEC, auditor and inspection by health authorities.

**9.10.3 Protocol deviations**

The investigators or sub-investigators will not develop or implement any deviation or change to the protocol without prior review by BI.

**10. PROTECTION OF HUMAN SUBJECTS**

The study will be carried out in compliance with the protocol, the principles laid down in the Declaration of Helsinki, Guidelines for Good Pharmacoepidemiology Practice (GPP), and the relevant BI Standard Operating Procedures (SOPs).

**10.1 STUDY APPROVAL, PATIENT INFORMATION, AND INFORMED CONSENT**

This NIS will be initiated only after all required legal documentation has been reviewed and approved by the respective Institutional Review Board (IRB)/Independent Ethics Committee (IEC) and Competent Authority (CA) according to national and international regulations. The same applies for the implementation of changes introduced by amendments.

**10.2 STATEMENT OF CONFIDENTIALITY**

Individual patient medical information obtained as a result of this study is considered confidential and disclosure to third parties is prohibited with the exceptions noted below. Patient confidentiality will be ensured by using patient identification code numbers.

Only anonymized data will be used in the study. Data generated as a result of the study need to be available for inspection on request by the participating physicians, the sponsor's representatives, by the IRB/IEC and the regulatory authorities.

**11. MANAGEMENT AND REPORTING OF ADVERSE EVENTS/ADVERSE REACTIONS**

**11.1 ADVERSE EVENT AND SERIOUS ADVERSE EVENT COLLECTION AND REPORTING****Collection of AEs**

This study is a non-interventional study based on secondary data without involving review or analysis of any individual patient level data. The data is extracted and analyzed in an aggregate manner. Therefore, from safety information collecting perspective, no AE/ADR collection & reporting of individual case safety reports is required. .

**11.2 REPORTING TO HEALTH AUTHORITIES**

Based on current guidelines from the International Society for Pharmacoepidemiology [R11-4318] and the European Medicines Agency (EMA) [R16-4913], non-interventional studies conducted using health care records do not require expedited reporting of suspected adverse events/reactions. Specifically, as stated in section VI.C.1.2.1 of GVP, Module VI – Management and Reporting of Adverse Reactions to Medicinal Products, for non-interventional study designs, which are based on use of secondary data, reporting of adverse reactions is not required.

This study is a non-interventional study based on secondary data, which will not involve individual medical record review. Therefore, no AE/ADR collection of this study will be performed and reported to Chinese regulatory authorities.

This study is classified as a PASS, and the study report will be reported to health authorities according to local regulations. The study results will also be reflected in the PSURs.

**12. PLANS FOR DISSEMINATING AND COMMUNICATING STUDY RESULTS**

The rights of the investigator and of the sponsor with regard to publication of the results of this study are described in the investigator contract. As a general rule, no study results should be published prior to finalization of the Study Report.

BI intends to use data from this study to prepare peer-reviewed publications and other scientific communications such as abstracts, posters, and podiums presentations.

The final report of the study result is planned in December 2021. Results of this PASS will be disclosed on [encepp.eu](http://encepp.eu) and [ClinicalTrials.gov](http://ClinicalTrials.gov).

# BOEHRINGER INGELHEIM Group of Companies

**NIS Protocol**

**BI Study Number 1160-0308**

Page 31 of 46

**ANNEX 1. LIST OF STAND-ALONE DOCUMENTS**

Number	Document Reference Number	Date	Title
1			

**ANNEX 2. ENCEPP CHECKLIST FOR STUDY PROTOCOLS**

Doc.Ref. EMA/540136/2009

**ENCePP Checklist for Study Protocols (Revision 4)**

Adopted by the ENCePP Steering Group on 15/10/2018

The European Network of Centres for Pharmacoepidemiology and Pharmacovigilance (ENCePP) welcomes innovative designs and new methods of research. This Checklist has been developed by ENCePP to stimulate consideration of important principles when designing and writing a pharmacoepidemiological or pharmacovigilance study protocol. The Checklist is intended to promote the quality of such studies, not their uniformity. The user is also referred to the ENCePP Guide on Methodological Standards in Pharmacoepidemiology, which reviews and gives direct electronic access to guidance for research in pharmacoepidemiology and pharmacovigilance.

For each question of the Checklist, the investigator should indicate whether or not it has been addressed in the study protocol. If the answer is "Yes", the section number of the protocol where this issue has been discussed should be specified. It is possible that some questions do not apply to a particular study (for example, in the case of an innovative study design). In this case, the answer 'N/A' (Not Applicable) can be checked and the "Comments" field included for each section should be used to explain why. The "Comments" field can also be used to elaborate on a "No" answer.

This Checklist should be included as an Annex by marketing authorisation holders when submitting the protocol of a non-interventional post-authorisation safety study (PASS) to a regulatory authority (see the Guidance on the format and content of the protocol of non-interventional post-authorisation safety studies). The Checklist is a supporting document and does not replace the format of the protocol for PASS presented in the Guidance and Module VIII of the Good pharmacovigilance practices (GVP).

